## DOCUMENT HISTORY

Version	Reason(s) for change	Date
V1.04	Initial document	30 June 2014
V1.05	Page 9, Section 3.2.2, last paragraph: changed font to Times New Roman 12 point. Page 15, Section 6.3.1, 3 rd line: substituted identity for logit as the link function.	21 July 2014

## PREFACE

This Statistical Analysis Plan (SAP) describes the planned analyses and reporting for the Australasian Kidney Trials Network (AKTN) protocol 08.01, a study designed to assess the feasibility of conducting a large randomised trial to determine whether the beta-blocker carvedilol reduces cardiovascular and all-cause mortality in patients receiving dialysis.

The structure and content of this SAP provide sufficient detail to meet the requirements identified by the International Conference on Harmonisation of Technical Requirements for Registration of Pharmaceuticals for Human Use (ICH): Guidance on Statistical Principles in Clinical Trials.(1) All work planned and reported for this SAP will follow national and international guidelines for statistical practice (2-5).

The planned analyses identified in this SAP will be included in future manuscripts. Exploratory analyses not necessarily identified in this SAP may be performed to support planned analyses. Any post-hoc or unplanned analyses not specified in this SAP will be clearly identified as such in the Full Statistical Report (FSR) and manuscripts for publication.

This SAP was written by a statistician and clinical investigators who were blinded to treatment allocation and treatment-related study results and will remain so until the central database is locked and the final data are extracted for analysis. To ensure blinding, treatment allocations are stored in a separate location accessible only by an un-blinded AKTN statistician.

The following documents were reviewed when preparing this SAP:

- Clinical Research Protocol for AKTN Trial Number 08.01 (6).
- Case report forms (CRFs) for AKTN Trial Number 08.01.
- Data Safety Monitoring Board (DSMB) Terms of Reference for AKTN Trial Number 08.01(7).
- ICH Guidance on Statistical Principles for Clinical Trials (1).
- ICH Guidance on Structure and Content of Clinical Study Reports (8).

Readers of this SAP are encouraged to read the Clinical Research Protocol for details on the conduct of this study and the operational aspects of clinical assessments and timing for completing a patient in this study.

## ABBREVIATIONS

ABBREVIATION	DEFINITION
ADR	Adverse Drug Reaction
AKTN	Australasian Kidney Trials Network
DSMB	Data and Safety Monitoring Board
ESKD	End-Stage Kidney Disease
FSR	Final Statistical Report
HD	Haemodialysis
ICH	International Conference on Harmonisation
IDH	Intradialytic hypotension
ITT	Intention-To-Treat
IVRS	Interactive Voice Response System
PD	Peritoneal Dialysis
SAE	Serious Adverse Event
SAP	Statistical Analysis Plan
TMC	Trial Management Committee

## **1. INTRODUCTION**

### **1.1 Background**

Cardiovascular disease is a major cause of morbidity and mortality in patients receiving dialysis (9, 10). However, current therapeutic strategies rely on extrapolation from randomised controlled trials conducted in people without end-stage kidney disease (ESKD). The increasing evidence of benefit from beta-blockers in randomised controlled trials in the general population may lead to more patients with end-stage kidney disease being prescribed beta-blockers, despite the absence of evidence for their use in this group, making future recruitment for a trial such as this more difficult. Thus, the present time is considered a window of opportunity in which to study this question.

There is insufficient data on the tolerability of carvedilol in the ESKD population and a feasibility study is a key step in performing a large trial. In addition to information on tolerability, a feasibility study will provide logistical data and data relevant to sample size estimation that will help plan the study.

### **1.2 Study synopsis**

The BLOCADE trial is a feasibility study for a large multi-centre, randomised, placebo-controlled trial of the effectiveness of the beta-blocker carvedilol to reduce cardiovascular morbidity and mortality in high-risk patients receiving dialysis. The multi-centre feasibility study had a six week active run-in period during which all participants received carvedilol. After the run-in period participants who tolerated carvedilol were randomised 1:1 to receive carvedilol (experimental intervention) or placebo (control intervention).

The BLOCADE feasibility study began recruiting patients on 16 May 2011 and stopped recruiting on 28 February 2013 due to slow recruitment and lack of funds to continue recruiting participants. In total, 88 participants from 11 sites were consented into the study. Of these, 72 participants from 9 sites entered the run-in phase and 49 participants from 8 sites were randomised. The final end-of-study visit was conducted in June 2014. The central database is expected to be available for analysis by the end of June 2014.

### **1.3 Sub-studies**

The BLOCADE feasibility trial has two sub-studies: the home blood pressure sub-study and the 24 hour ambulatory blood pressure monitoring sub-study. Statistical analyses for these sub-studies are not described in this SAP.

## **2. STUDY OBJECTIVES**

### **2.1 Primary objectives**

The primary objective is to determine the feasibility and to inform the design of a larger clinical end-point study by measuring factors relevant to three aspects of planning a larger study:

- 1) Tolerability of carvedilol
- 2) Sample size for a clinical end-point study
- 3) Logistics of a larger study

## 2.2 Secondary objectives

Secondary objectives are to examine the effect of therapy with carvedilol compared to placebo on change in B-type natriuretic peptide (BNP) and change in quality of life. In addition, baseline BNP as a predictor of response to carvedilol will be assessed, where response is defined as failure to complete the run-in phase for any reason.

## 2.3 Tertiary (exploratory) objectives

Exploratory objectives include assessment of intradialytic hypotension during run-in and in response to random allocation to treatment.

## 3. STUDY DESIGN ISSUES

### 3.1 Overview

The BLOCADE trial is a phase III, randomised, double-blind, placebo-controlled, parallel group feasibility study with a six week open-label active run-in phase during which all participants received carvedilol up to a maximum dose of 6.25 mg twice daily. Participants who tolerated this dose for at least two weeks prior to the randomisation visit were randomised to carvedilol or placebo. After randomisation, participants were up-titrated to a maximum dose of 25 mg twice daily of carvedilol or placebo over a period of six weeks (plus another 4 weeks if needed), then followed for 12 months before being down-titrated off study drug over a period of four weeks.

### 3.2 Study population

The population of interest is patients receiving either haemodialysis (HD) or peritoneal dialysis (PD) at hospitals in Australia and New Zealand.

#### 3.2.1 Inclusion criteria

Patients were eligible for inclusion in the trial if all of the following criteria were met:

- 1) The person was willing to participate and had signed the Participant Information and Consent Form
- 2) The person had end-stage kidney disease and was receiving either haemodialysis or peritoneal dialysis
- 3) At the time of signing the consent form, the person met the following:
  - i) Age  $\geq$ 50 years, OR
  - ii) Age  $\geq$ 18 years with diabetes, OR
  - iii) Age  $\geq$ 18 years and has clinical features of cardiovascular disease (myocardial infarction or ischaemic heart disease, ischaemic stroke or peripheral arterial disease)

as determined by the site investigator and defined in the **Appendix (Section 13.2)** of the BLOCADE Trial Protocol (6).

- 4) The treating nephrologist agreed the person could participate in the BLOCADE Feasibility Study

### 3.2.2 Exclusion criteria

Patients were excluded from the study if any one of the following conditions was met:

- 1) Scheduled for live donor transplant within six months.
- 2) Experienced a cardiovascular event in the previous 3 months. Cardiovascular events include: myocardial infarction, admission for unstable angina, coronary revascularisation procedure, peripheral arterial revascularisation procedure or stroke.
- 3) Definite contra-indication to beta-blockers, such as:
  - a) 2nd or 3rd degree atrioventricular block unless treated with a permanent pacemaker
  - b) sick sinus syndrome unless treated with a permanent pacemaker
  - c) clinically significant reversible bronchospasm
  - d) previous intolerance to beta-blockers
  - e) other contra-indication
- 4) Currently taking a **beta-blocker, verapamil, diltiazem or moxonidine** and the treating nephrologist does not wish to stop these medications in order to enter the trial.
- 5) Considered by the treating nephrologist to be clinically or haemodynamically unstable for the study.
- 6) Unstable target weight (defined by a change of  $\geq 2.0$ kg in target base weight over the preceding month).
- 7) Severe hepatic dysfunction (transaminases  $\geq 3$ x higher than the upper normal limit) on the most recent liver function tests (if performed within 3 months).
- 8) Already involved in a clinical trial where the intervention being trialled is likely to confound the outcome of this trial.
- 9) Considered by the treating physician to have a life expectancy of less than 12 months.
- 10) Inability to provide consent or follow study instructions due to psychological illness or other condition.
- 11) Pregnant or planning to be pregnant during the trial period.

The eligibility criteria were more restrictive at the start of the trial. In an attempt to improve recruitment, protocol amendments on 8 March 2012 removed one inclusion criterion (The person has been receiving dialysis for more than 3 months but less than 36 months at the time of signing the consent form) and one exclusion criterion (Aged 75 or older at the time of signing the consent form).

### 3.3. Sample size

The planned sample size was 150 patients to enter the run-in phase. This number was based on a confidence interval approach for estimating the proportion of patients who would tolerate carvedilol during the run-in phase. Assuming a tolerability of 70%, 150 patients would give 95% confidence limits of 62.5% and 77.5%. Due to slow recruitment and diminished funds, recruitment was prematurely stopped after 88 participants had been

consented into the study. Of these, 72 entered the run-in phase (48% of the target sample size).

### **3.4 Treatment allocation**

Participants who tolerated a twice daily 6.25 mg dose of carvedilol by the end of the run-in phase were randomised 1:1 to one of the two treatment groups. Randomisation was conducted using an interactive voice response system (IVRS). The IVRS randomised patients by an adaptive allocation algorithm designed to minimise study site and dialysis modality (haemodialysis or peritoneal dialysis) imbalance within the two treatment groups.

### **3.5 Treatment blinding and allocation concealment**

Investigators and participants were blinded to randomised treatment assignment. Performing randomisation using an IVRS provided by the National Health and Medical Research Council Clinical Trials Centre in Sydney, Australia, ensured concealment of treatment allocation from site staff, who were responsible for performing the EQ5D, recording IDH over specific times and reporting SAEs. The three clinical end-point adjudicators adjudicated possible cardiovascular events during the course of the study and were also unaware of treatment assignment. Biochemistry staff in contracted laboratories who will perform outcome assessments such as measurement of BNP and other markers will be blinded to the treatment allocations.

### 3.6 Schedule of assessments

STUDY PHASE	BA	RUN-IN*			RA	TITRATION*					FOLLOW-UP*				END OF STUDY*		
		R0	R2	R4		T2	T4	T6	T8 ^	T10 ^	F3	F6	F9	F12	E2	E4	E6 #
Assessment:																	
History	X																
Examination	X																
Height	X																
Heart Rate	X	X	X	X	X	X	X	X	X	X	X	X	X	X	X	X	X
Blood Pressure	X	X	X	X	X	X	X	X	X	X	X	X	X	X	X	X	X
ABPM (optional)	X											X					
IDH			X			X	X				X	X					
Home BP (optional)	X	X	X	X	X	X	X	X	X	X	X	X	X				
Dry weight	X	X			X						X	X	X	X	X	X	X
Concomitant medications	X	X	X	X	X	X	X	X	X	X	X	X	X	X	X	X	X
Study drug dispensed		X	X	X	X	X	X	X	X	X	X	X	X	X	X	X	
ECG	X										X			X			
ECHO		X															
BNP		X										X		X			
Laboratory studies		X			X							X		X			
Quality of Life (EQ5D)	X											X		X			
Serious Adverse Events & Adverse Drug Reactions			X	X	X	X	X	X	X	X	X	X	X	X	X	X	X

BA=Baseline assessment, R0-R4 (weeks)=Run-in phase, RA=Randomisation visit, T2-T10 (weeks)=Titration phase, F3-F12 (months)=Follow-up phase, E2-E6 (weeks)=End of Study. \*Visit Windows: Run-in =  $\pm 4$  days; Titration =  $\pm 4$  days; Follow-up =  $\pm 1$  week; End of Study =  $\pm 4$  days. ^Only if required. #Study Coordinator will contact participant by telephone 1 month after complete cessation of study drug to ascertain vital status and determine if adverse events occurred during this period. All assessments were to be conducted before a patient commenced their dialysis session. For haemodialysis patients, assessments were to be conducted after their "short break".

## 4. STUDY OUTCOME VARIABLES

### 4.1 Primary outcomes

A range of outcome measures were considered primary in order to assess the feasibility of a clinical end-point study with carvedilol as the intervention. These were:

- 1) Tolerability
  - a. The proportion of participants who finish the run-in phase on a twice daily dose of carvedilol of at least 6.25 mg. Participants who enter run-in but do not take any study medication will be counted among those who fail to finish run-in. Those who do not finish the run-in phase as defined above will be classified as a carvedilol-related failure or a failure for other reasons.
  - b. The proportion of participants randomised to carvedilol (placebo) that drop out due to any adverse event attributable to the study product.
  - c. The incidence of major adverse events of symptomatic hypotension and symptomatic bradycardia in participants randomised to carvedilol (placebo).
- 2) Sample size
  - a. The proportion of participants randomised to carvedilol (placebo) that cease study medication for any reason.
  - b. The Proportion of participants randomised to carvedilol (placebo) that are thought to require beta-blocker therapy after randomisation.
  - c. The proportion of participants who withdraw consent to participate in the study after randomisation.
  - d. Overall post-randomisation rate of the proposed composite primary outcome for the clinical end-point study (cardiovascular death, non-fatal myocardial infarction, non-fatal stroke, resuscitated cardiac arrest).
  - e. Overall post-randomisation rate of proposed secondary outcomes for the clinical end-point study (all-cause mortality, the composite primary outcome plus hospital admission for cardiovascular disease, total days in hospital, total days in hospital where cardiovascular disease is the main reason for admission).
- 3) Logistics
  - a. Recruitment rate (number per month)
  - b. The proportion of screened patients eligible for run-in.
  - c. The proportion of participants eligible for run-in who enter run-in.
  - d. The proportion of participants randomised to carvedilol (placebo) that are on a dose of 25 mg twice daily at each titration and follow-up visit.

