### 6.3.3 Logistics

Recruitment rate will be represented graphically by plotting monthly recruitment and cumulative recruitment numbers at each month of active recruitment. Proportions and 95% confidence intervals for screened patients eligible for run-in and eligible patients who entered run-in will be estimated as described above for tolerability outcome variables. Proportions randomised to carvedilol and placebo on a 25 mg dose during each titration and follow-up visit will be separately analysed for each treatment group using a mixed-effects logistic regression model with study visit as a fixed effect in the model and participant identifier as a random effect. Proportions on each dose of study drug (6.25 mg, 12.5 mg, 25 mg) by treatment group across titration and follow-up visits will be described.

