### 8.1 Planned tables

The following are planned summary tables:

- Table 1. Reasons screened patients were not consented into the study
- Table 2. Enrolment by study centre
- Table 3. Stratification variables by treatment group for randomised participants
- Table 4. Withdrawals, protocol deviations and violations during run-in
- Table 5. Withdrawals, protocol deviations and violations by treatment group
- Table 6. Demographic and clinical baseline characteristics for participants who entered run-in, overall and by successful completion of run-in (yes, no) [Table note indicating 16 consented participants did not enter run-in]
- Table 7. Demographic and clinical baseline characteristics by final run-in dose for all participants who entered run-in
- Table 8. Demographic and clinical baseline characteristics by treatment group for randomised participants
- Table 9. Number (percent) for primary outcomes of feasibility, sample size and logistics
- Table 10. Number of proposed primary and secondary outcomes for large clinical endpoint study
- Table 11. Intradialytic hypotensive episodes per dialysis session during run-in
- Table 12. Intradialytic hypotensive episodes per dialysis session overall and by treatment group for randomised participants
- Table 13. Number (percentage) of dialysis sessions during which an intradialytic hypotensive event occurred during run-in
- Table 14. Number (percentage) of dialysis sessions during which an intradialytic hypotensive episode occurred overall and by treatment group for randomised participants
- Table 15. SAEs and ADRs during run-in, overall and by successful completion of run-in (yes, no)
- Table 16. SAEs and ADRs by treatment group for randomised participants

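### The recruitment-rate outcome (3a) has no site-time denominator, so it mixes the number of open sites with the yield per open site and does not scale reliably to a larger trial

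*SAP*

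**What the plan says.** Section 2.1 sets the purpose: "The primary objective is to determine the feasibility and to inform the design of a larger clinical end-point study". The logistics of that larger study are the third of its three aspects.

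Section 4.1 lists the first logistics outcome (3a) as "Recruitment rate (number per month"), with no mention of sites. Section 6.3.3 gives its whole analysis: "Recruitment rate will be represented graphically by plotting monthly recruitment and cumulative recruitment numbers at each month of active recruitment". Section 8.3 repeats this as Figure 1. No rate is estimated, no interval is planned, and the counted event (consent, run-in entry or randomisation) is not named for 3a.

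Two other places bear on the point. Section 1.2 says that the study "began recruiting patients on 16 May 2011 and stopped recruiting on 28 February 2013" and that "88 participants from 11 sites were consented into the study". It adds that 72 participants from 9 sites entered run-in and 49 from 8 sites were randomised. Section 8.1 plans "Table 2. Enrolment by study centre", of which only the title is shown; section 8 says that the table templates are in a separate document.

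The SAP shown contains no plan to collect or report site opening dates, site-months or a per-site rate.

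**The concern.** Whole-trial recruitment per month depends on how many sites were open and for how long, as well as on how fast an open site recruits. The first two describe this feasibility study. The third is what a planner carries to a trial with a different number of sites, and 3a does not separate it out.

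This matters because section 1.2 gives slow recruitment, together with lack of funds, as the reason for stopping. A monthly total cannot show whether open sites recruited poorly or whether sites opened late. The first calls for more sites or wider eligibility; the second calls for faster start-up. A projection built on the wrong explanation misjudges the length of the larger trial.

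**Working it through.** **Plan's own figure.** The SAP states no recruitment rate, so there is none to reproduce. Its related counts agree: 72/150 = 48% (section 3.3), and 88 − 72 = 16 consented but not entering run-in (sections 8.1 and 8.2).

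**Inputs (section 1.2).** Recruitment ran from 16 May 2011 to 28 February 2013. There were 88 consents from 11 sites, 72 run-in entries from 9 and 49 randomisations from 8. Site opening and closing dates are not given.

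**Period.** 655 days counting both end dates; 655 / 30.4375 = 21.52 months.

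**Outcome 3a as listed** (count / months):

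| Event counted | Calculation | Per month |
|---|---|---|
| Consent | 88 / 21.52 | 4.09 |
| Run-in entry | 72 / 21.52 | 3.35 |
| Randomisation | 49 / 21.52 | 2.28 |

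The answer depends on which event is meant.

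**Per site-month** = count / (sites × months × average fraction of the period open). The fraction open is an assumption in every row, and 11 sites are used throughout:

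| Average fraction open | Site-months | Consents | Randomised |
|---|---|---|---|
| 100% | 11 × 21.52 = 236.7 | 88 / 236.7 = 0.37 | 49 / 236.7 = 0.21 |
| 75% | 177.5 | 0.50 | 0.28 |
| 50% | 118.4 | 0.74 | 0.41 |

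The exact Poisson 95% interval for the 0.37 is 0.30 to 0.46. The 0.74 lies well outside it, so not knowing the time open can matter more than chance.

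**Sites with no recruits.** The 11 sites are those that consented someone. If two more had been open throughout with no recruits (assumption), the rate would be 88 / (13 × 21.52) = 0.31.

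**Contributing sites are a poor denominator.** 88/11 = 8 and 72/9 = 8, so dividing each count by its own contributing sites gives 0.37 per site-month for both consent and run-in entry. That hides the loss of 16 participants between the two steps. With 11 sites for both, run-in entry is 72 / 236.7 = 0.30.

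**Consequence, for illustration.** Assume 50 sites and 1,000 consents. At 0.37 per site-month the trial gains 50 × 0.3718 = 18.6 consents per month and takes 1,000 / 18.6 = about 54 months. At 0.74 it gains 37.2 per month and takes about 27 months. Outcome 3a reads 4.1 consents per month in both cases.

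**Eligibility change.** Section 3.2.2 dates the widening of eligibility to 8 March 2012. That splits the period into 297 days (9.8 months) and 358 days (11.8 months), so one pooled rate covers two sets of criteria.

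**The case against.** The best defence is that nothing here is wrong or inconsistent. Number per month is a legitimate descriptive measure, and sections 4.1, 6.3.3 and 8.3 agree with one another. The outcome may come from a protocol that is not shown, since section 5.3 reports no important changes from it. The per-site rate could be worked out later from site records, and the Preface and section 5.2 already allow labelled additional analyses. This stands as a limit on severity: no treatment comparison or error rate is affected. It does not answer the point that the measure chosen for a primary outcome serves its stated purpose poorly.

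Three stronger readings are tempting but not supported:

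- *That recruitment cannot be scaled at all.* Section 1.2 gives dates and site counts, and enrolment by centre is planned, so a crude per-site rate is available. What is missing is the time open that would make it reliable.
- *That Table 2 omits time open or sites with no recruits.* Only its title is shown. The template could include both.
- *That the SAP fixes a calendar-month denominator.* It refers to months of active recruitment, without saying whether this means the trial or its sites. Either way, no site term appears.

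It is also fair to object that the twofold range comes from the assumed 50% to 100% opening, and that the 50 sites and 1,000 consents are not in the SAP. They show how sensitive the projection is, not the size of an actual error.

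Last, a per-site rate alone would still mix two eligibility periods, and a simple Poisson interval over about 11 sites could look too precise. Both objections are right and are met in the fix.

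**Conclusion.** The point holds as a weakness in the chosen measure. Outcome 3a, as defined and analysed, combines the number of open sites with the yield per open site and cannot be reliably carried to a trial with a different number of sites. The crude 0.37 consents per site-month rests on all 11 consenting sites being open for the full 21.5 months and on no other site having opened. Average opening of 50% would double it to 0.74; opened sites without recruits would pull it down. The true value cannot be found from the SAP.

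A reader might infer that the recruitment results would be unusable or that a stated figure is wrong. Neither follows: the number per month remains valid as a description of this trial. The label is a cheap improvement.

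**What to change.** Keep the number per month as listed. In section 4.1 (3a) and section 6.3.3, add the following:

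- **Rate.** Participants consented, entering run-in and randomised, each per active site-month.
- **Denominator.** The sum, over all opened sites including any with no recruits, of the months from opening to closure or 28 February 2013, whichever came first.
- **Interval.** A 95% interval that allows for variation between sites, for example from a negative binomial model with log site-months as offset, or from resampling whole sites.
- **Periods.** The rate before and after the 8 March 2012 eligibility change, as well as overall.
- **Figure 1.** The number of open sites in each month, plotted with monthly and cumulative enrolment.

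The cost is a few lines of SAP text, a small extra analysis, and site opening and closing dates, which the coordinating centre should hold. No new patient data are needed. The final analysis was still ahead when the SAP was written, and the rate does not use treatment allocation, so the late addition does not threaten any comparison. The drawback is that with about 11 sites the interval will be wide.
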